6.1.6. Storage and Stability

Kits containing sachets of study drug will be stored at room temperature (~15 to 30°C). The available stability data from representative samples support the use of the drug product for 48 months when stored at room temperature. The stability of the clinical study samples or representative samples will be monitored to support the clinical study, as necessary.

6.1.7. Study Drug Accountability

Study personnel must ensure that all study drug supplies are temperature monitored and kept in a secure locked area with access limited to authorized personnel. This study product must not be used outside the context of this protocol. Under no circumstances should the investigator or site personnel supply study product to other investigators or clinics, or allow the supplies to be used other than as directed by this protocol.

The investigator and/or the responsible site personnel must maintain accurate records of the receipt of all study drug shipped by PTC Therapeutics or its designee, including, but not limited to, the date received, lot number, amount received, and the disposition of all study drug. Current reconciliation and dispensing records must also be maintained that include the date and amount of drug dispensed, and patient's assigned study number.

Depending upon the decision of PTC Therapeutics, unused clinical supplies must be destroyed or must be returned to PTC Therapeutics or its designee after the study is completed. Accountability must be verified by the site monitor prior to return or destruction. Records documenting the date of study drug destruction or shipping, relevant sachet numbers, and amount destroyed or shipped should be kept in the investigator site study file.

6.1.8. Overdose Precautions

For any patient experiencing an overdose (administration of a study drug dose >4 times the highest intended total daily dose level for this protocol [>160 mg/kg/day]), observation for any symptomatic side effects should be instituted, and vital signs and biochemical and hematological parameters should be followed closely (consistent with the protocol or more frequently, as needed). Appropriate supportive management to mitigate adverse effects should be initiated. Pending the acquisition of sufficient human experience with the drug, use of gastric lavage or induction of emesis is not specifically recommended nor contraindicated.

The PTC Therapeutics medical monitor must be contacted if an overdose occurs. Under applicable regulations, overdosing may be considered an SAE and should be reported accordingly (see Sections 9.1.1 and 9.1.2).

6.1.9. Inadvertent Exposure and Spill Precautions

Reference can be made to the Ataluren Investigator Brochure for current information on inadvertent exposures and spill precautions.

6.2. Study Drug Treatment

6.2.1. Duration of Treatment

In this study, treatment will comprise continuous daily treatment with ataluren for up to 96 weeks (~2 years). This study may be further extended by amendment until either ataluren

becomes commercially available or the clinical development of ataluren in nmCF is discontinued.

6.2.2. Schedule of Administration

As noted in Table 1, 3 doses should be taken per day – the 1st dose in the morning, the 2nd dose during the middle of the day (mid-day), and the 3rd dose in the evening. Ideally each dose should be taken within ~30 minutes before or after a meal (eg, ~7:00 AM after breakfast, ~1:00 PM after lunch, and ~7:00 PM after dinner). Intervals for dosing should be ~6 hours (\pm 1 hour) between morning and mid-day doses, ~6 hours (\pm 1 hour) between mid-day and evening doses, and ~12 hours (\pm 1 hour) between evening doses and the morning dose on the next day. While it is realized that variations in dosing schedule may occur in the outpatient setting, the prescribed regimen (including dosing intervals and the relationship of dosing to meals) should be followed closely on the day preceding PK sample collection in the clinic.

Table 1. Suggested Daily Dosing Schedule								
Dose Designation	Preceding Meal	Example Dosing Times ^a						
Morning	Breakfast	~7:00 AM – 0700 hours (±1 hour)						
		\uparrow						
		~6 hours						
		\downarrow						
Mid-day	Lunch	~1:00 PM – 1300 hours (±1 hour)						
		\uparrow						
		~6 hours						
		\downarrow						
Evening	Dinner	~7:00 PM – 1900 hours (±1 hour)						
		\uparrow						
		~12 hours						
		\downarrow						
Next Day Morning	Breakfast	7:00 AM – 0700 hours (±1 hour)						

Table 1. Suggested Daily Dosing Schedule

a Dosing times are examples and may be varied to suit each patient's schedule. However, the time between morning and midday doses and between midday and evening doses should be maintained at ~6 hour intervals, while the time between the evening and next morning dose should be maintained at an ~12 hour interval.

6.2.3. Instructions for Delays in Dosing

If a patient experiences a delay in the administration of study drug of ≤ 1 hour, the planned dose should be taken with no changes to the subsequent dose schedules. For a patient who has a delay of >1 hour but ≤ 4 hours, the planned dose should be taken; however, all future doses for that day should be shifted later by an approximately corresponding amount. For a patient who has a delay in administration of study drug of >4 hours, the dose should not be taken. Study drug administration may continue but the missed dose should not be made up and the planned timing of subsequent study drug dosing should not be altered.

6.2.4. Study Drug Preparation and Storage

Study drug sachets should be stored at room temperature, away from the reach of children until time of reconstitution and should only be opened at the time of dose preparation. The powder in the sachet may be mixed with water, milk (skim, 1% fat, 2% fat, whole milk, chocolate milk,

soy, or lactose free milk), or in semi-solid food (yogurt, pudding, or applesauce). The full contents of the sachets should be mixed with at least 30 mL (1 ounce) of liquid (water, milk [skim, 1% fat, 2% fat, whole milk, chocolate milk, or lactose-free milk], or 3 tablespoons of semi-solid food (yogurt, pudding, or applesauce). The prepared dose should be mixed well before administration. The amount of the liquid or semi-solid food can be increased based on patient preference.

Each prepared dose is best administered immediately after preparation. The prepared dose should be discarded if not consumed within 24 hours of preparation if kept refrigerated, or within 3 hours of preparation if kept at room temperature.

The clinic staff will instruct each subject or parent/caregiver on the specific number of sachets to be taken from each kit for each dose and will provide detailed oral directions regarding drug preparation. In addition, detailed written drug mixing and dosing instructions will be provided to the subject or parent/caregiver when drug supplies are dispensed.

6.3. Safety Monitoring and Study Drug Dose Interruption/Modification

6.3.1. Laboratory Abnormalities and Adverse Events Requiring Evaluation and Potential Drug Interruption/Modification

Patients must be monitored closely for adverse events or laboratory abnormalities during the course of the study.

For adverse events or laboratory abnormalities, the investigator will use judgment in determining whether the event or abnormality is clinically significant, whether diagnostic evaluation is warranted, and whether potential interruption of study drug treatment is appropriate. In general, life-threatening (Grade 4) or severe (Grade 3) adverse events or laboratory abnormalities should be considered clinically significant, although recurrent or persistent moderate events (Grade 2) may also be considered clinically significant in certain circumstances. Reference should be made to the Common Terminology Criteria for Adverse Events (CTCAE), Version 3.0 (see *http://ctep.cancer.gov/protocolDevelopment/electronic_applications/docs/ctcaev3.pdf* for grading the severity of adverse events and laboratory abnormalities.

Table 2 provides information on actions to be taken in the event that abnormalities are noted in specified laboratory parameters. Thresholds are provided for interrupting study drug immediately, for interrupting study drug after confirmation of a value beyond the threshold, or for continuing study drug while evaluating for potential drug-related toxicity. For adverse events or laboratory abnormalities not listed in Table 2, the investigator should use his/her judgment in determining whether the event or abnormality is clinically significant, whether diagnostic evaluation is warranted, and whether potential interruption of study drug is appropriate.

Organ System and Laboratory Parameter	Stop Study Drug Immediately, Confirm Abnormal Value, and Then Start Work-Up ^a	Stop Study Drug After Confirming Abnormal Value, and Then Start Work-Up ^a	Continue Study Drug, Confirm Abnormal Value, and then Start Work-Up ^a
Hepatic			
Serum total bilirubin ^b	≥Grade 3 (≥3.0 x ULN)	Grade 2 (1.5 – 3.0 x ULN)	
Serum ALT	≥Grade 3 (≥5.0 x ULN)	Grade 2 (>2.5 – 5.0 x ULN)	
Serum AST	≥Grade 3 (≥5.0 x ULN)	Grade 2 (>2.5 – 5.0 x ULN)	
Serum GGT	≥Grade 3 (≥5.0 x ULN)	Grade 2 (>2.5 – 5.0 x ULN)	
Renal			
Serum cystatin C	>2.00 mg/L	>1.33 – 2.00 mg/L	
Serum creatinine	≥ Grade 2 (≥1.5 x ULN for	Grade 1 (>ULN – 1.5 x ULN for	
Serum creatinine	age)	age)	
Serum BUN	≥3.0 x ULN	≥1.5 – 3.0 x ULN	

Table 2. Safety Monitoring Parameters and Actions To Be Taken

^a Laboratory abnormalities may be confirmed immediately or at the next scheduled clinic visit based on investigator judgment.

^b Patients with a diagnosis of Gilbert's syndrome need not confirm the laboratory parameter and/or stop study drug unless the total bilirubin value exceeds 3.0 x ULN.

Abbreviations: ALT = alanine aminotransferase, AST = aspartate aminotransferase, BUN = blood urea nitrogen, GGT = gamma glutamyl transferase, ULN = upper limit of normal

It should be noted that blood samples for cortisol, renin and aldosterone determinations will be obtained at screening, and, as necessary during the study, for patients with treatment-emergent evidence of adrenal dysfunction.

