7.1.2. Therapy for CF Pulmonary Exacerbations or Other CF Complications

Patients should receive appropriate antibiotic or other therapy for CF pulmonary exacerbations or other CF-related complications (eg, DIOS) consistent with local best practices and guidelines. For patients requiring systemic antibiotic therapy, IV aminoglycosides may be used when medically necessary. However, given ataluren's ribosomal mechanism of action, and the possibility of aminoglycosides exhibiting a confounding effect upon study results, investigators should substitute other antibiotics for systemic aminoglycosides in patients who require treatment for serious infections whenever possible. For such severe infections, consideration should be given to use of appropriate alternative anti-pseudomonal agents including macrolide and glycopeptide antibiotics. Patients requiring IV therapy with an aminoglycoside or glycopeptide antibiotic (eg, vancomycin), should be closely monitored in an appropriate setting. Particular caution should be used for patients with a previous history of clinically significant creatinine elevations. Based on the increased incidence of creatinine elevation in patients treated with IV aminoglycosides and/or vancomycin, concomitant use of these medications with ataluren is contraindicated. If nephrotoxic antibiotics (eg, tobramycin or vancomycin) are administered, ataluren treatment must be interrupted for the duration of IV antibiotic treatment. In patients receiving any type of potentially nephrotoxic antibiotics, antibiotic drug levels, and renal function should be closely monitored. Creatinine and BUN should be measured prior to initiating IV aminoglycosides or other potentially nephrotoxic therapy, and at least twice a week during the course of such antibiotic treatment. The antibiotic trough level, creatinine and BUN

should be measured within 24 to 48 hours of administration of the first antibiotic dose, and further antibiotic dosing should be based on these results. Trough levels should also be measured at intervals during the course of antibiotic treatment.

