11.3. General Statistical Considerations

By-subjects listings will be created for each CRF module. Summary tables for continuous variables will contain the following statistics: n, mean, standard deviation, standard error, 95% confidence intervals (CIs) on the mean, median, minimum, and maximum. Summary tables for categorical variables will include N, n, percentage, and 95% CIs on the percentage. Where applicable, the summary data (mean, standard error) will be presented in graphical form of against time of visit.

Unless otherwise specified, all analyses will be 2-sided at the 0.05 level of significance.

All analyses will be performed based on all observed data. For the efficacy endpoints, eg, FEV₁, FVC, FEF₂₅₋₇₅, and pulmonary exacerbation, the analyses will be performed for 48-week completers and the whole study completers as well.

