In the Phase 3 clinical trial (Study 009), serious adverse events related to renal dysfunction, which occurred only in the ataluren arm, included 3 patients with acute renal failure, 3 patients with renal failure, and 1 patient with hypercreatininemia. These events were characterized by elevated creatinine (Grade 1 to Grade 4), which resolved over days to weeks. Only 1 patient experienced symptoms of renal dysfunction (transient oliguria). All 7 events were associated with concomitant systemic treatment with potentially nephrotoxic antibiotics (eg, aminoglycosides, vancomycin) that were generally administered as treatment for pulmonary exacerbations. No patient required dialysis. One patient was unblinded and 1 patient chose not to continue study drug treatment; the remaining 5 of 7 patients restarted study medication and continued study participation without recurrent creatinine elevations. This issue was recognized during the conduct of the study and changes were made in the protocol (eg, prohibition of concomitant use of potentially nephrotoxic agents), which successfully addressed the issue.

Non-serious creatinine elevations occurred predominantly in the ataluren arm and were transient, generally mild, and resolved with or without interruption of study medication. The incidence of treatment emergent nephrolithiasis was similar in the ataluren and placebo groups.

Non-serious episodes of creatinine elevation in Study 009 occurred predominantly in the ataluren arm and were transient, generally mild, and resolved with or without interruption of study medication. However, there was no clinically meaningful difference in creatinine between the ataluren and placebo arms at Week 48, indicating that there was no cumulative effect of these transient elevations on renal function. The incidence of treatment-emergent nephrolithiasis was similar in the ataluren and placebo groups.

The renal monitoring program included in this protocol considers nonclinical and clinical findings with ataluren and past experience with known nephrotoxicants. Concomitant use of potentially nephrotoxic antibiotics with ataluren is prohibited. A focus is placed on well-established clinical indictors of renal dysfunction for making diagnostic decisions and prompting treatment interruptions/ modifications in individual patients. The rationale for each of the decision-making parameters is discussed below.

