14.2.8. Other Abnormalities

Recommendations for interruption of dosing are provided in Section 6.3.1, with the general intent that a Grade 4 (life-threatening) event should result in immediate cessation of study drug while awaiting confirmation of the abnormal laboratory value, a Grade 3 (severe) event may require confirmation of the abnormal laboratory value before cessation of dosing, and a Grade 2 (moderate) event may prompt further evaluation while study drug dosing continues. It is intended that these recommendations be viewed flexibly; the type and context for any adverse event or laboratory abnormality must be considered in taking action.

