4.10.2. Clinical Laboratory Evaluations

Hematology laboratory assessments will include white blood cell count with differential, hemoglobin, hematocrit, mean corpuscular volume, mean corpuscular hemoglobin, mean corpuscular hemoglobin concentration, total red cell count with morphology, and platelet count. These parameters will be measured at all study visits.

Biochemistry laboratory assessments will include sodium, potassium, chloride, bicarbonate, blood urea nitrogen, creatinine, magnesium, calcium, phosphorus, uric acid, glucose, total protein, albumin, globulin, albumin:globulin ratio, bilirubin (total, direct and indirect), creatine kinase (CK), lactate dehydrogenase (LDH), alanine aminotransferase (ALT), aspartate aminotransferase (AST), gamma glutamyl transferase (GGT), alkaline phosphatase, total cholesterol, high-density lipoprotein (HDL), low-density lipoprotein (LDL), triglycerides, and cystatin C. These parameters will be measured at all study visits. Ideally, subjects should have fasted for at least 8 hours prior to blood collection.

Urinalysis assessments will include pH, specific gravity, glucose, ketones, blood, protein, creatinine, urobilinogen, bilirubin, nitrite, and leukocyte esterase. These parameters will be measured at all study visits.

Hematology, serum biochemistry, and urinalysis data and their changes from baseline (only for continuous laboratory parameters) will be summarized by visit. Maximal and minimal change from baseline in each parameter will also be summarized.

Shift tables for hematology, serum biochemistry, and urinalysis will also be presented showing change in CTCAE severity grade from baseline to each visit. For parameters for which a CTCAE scale does not exist, shift tables will be presented showing change in results from baseline (normal, low, and high [or abnormal]) to each visit (normal, low, and high [or abnormal]).

Frequency tables will be presented for safety monitoring parameters to show the number and percentages of subjects by severity grade categories defined in Table 2. If a CTCAE grade does not exist, abnormal results will be summarized by protocol-defined thresholds as noted in Table 2. Subjects will be characterized only once for a given assay, based on their worst severity grade observed during the time period of interest.

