5.2. Analysis Visits

Analysis visits are the scheduled visits in the protocol, unless specified otherwise. They are not derived via visit window mapping. Baseline is derived as noted in Section 5.1. Final Visit is derived as the last non-missing on-treatment visit during the study for each subject and included into the by-visit summary analyses. Early termination visit should also be derived as the visit right after the non-missing scheduled visit. For example, if the subject discontinued after Week 12, the early termination visit should be derived as Week 24.

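### For the seven Table 2 hepatic and renal parameters, the by-visit laboratory tables mix on-drug and off-drug samples, and no firmly planned table shows the time course of first abnormality on ataluren

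*Protocol*

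**What the plan says.** **Stopping rule.** Protocol 6.3.1 says of Table 2: "Thresholds are provided for interrupting study drug immediately, for interrupting study drug after confirmation of a value beyond the threshold". The parameters are total bilirubin, ALT, AST, GGT, cystatin C, creatinine and BUN. A footnote adds: "Laboratory abnormalities may be confirmed immediately or at the next scheduled clinic visit based on investigator judgment". Protocol 14.2.8 says of the 6.3.1 recommendations: "It is intended that these recommendations be viewed flexibly". Separately, Protocol 7.1.2 requires that, when nephrotoxic IV antibiotics are given, "ataluren treatment must be interrupted for the duration of IV antibiotic treatment".

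**Tabulation.** Protocol 11.3: "All analyses will be performed based on all observed data". SAP 4.10.2 says laboratory values and changes from baseline "will be summarized by visit. Maximal and minimal change from baseline in each parameter will also be summarized", and adds shift tables from baseline to each visit. SAP 5.2: "Analysis visits are the scheduled visits in the protocol, unless specified otherwise". In these visit rules only the derived Final Visit carries an on-treatment condition, and the term is not defined for interruptions. An early-termination value goes into the row after the last scheduled visit with data. Protocol 8.2.5 allows for an End-of-Treatment visit more than 4 weeks after the last dose.

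**Other tables.** SAP 4.10.2 plans a worst-grade table, one entry per subject and assay, for the Table 2 parameters. Abnormalities by duration of exposure are to be described only as necessary. SAP 4.9 computes treatment duration without subtracting interruptions. The exposure-adjusted rates in SAP 4.10.1 are for treatment-emergent adverse events. SAP 2.3.1 includes timing in the primary endpoint, which covers laboratory abnormalities.

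**The concern.** Whether a patient is on ataluren at a given visit depends partly on the value being tabulated. Visits are 12 weeks apart, and Protocol 14.2.4 reports that the renal serious events in Study 009 resolved over days to weeks. A patient stopped for raised creatinine and still off drug at the next visit can therefore contribute a recovered value to a treatment-period row, with nothing to mark it as off drug.

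Early termination adds a second route. SAP 2.1 says that ongoing subjects will be discontinued, so many rows may hold relocated early-termination values whose distance from the last dose is not checked.

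The by-visit tables are the main planned view of laboratory change over time in a long-term safety study. Protocol 14.2.4 already reads a Week 48 comparison in Study 009 as "indicating that there was no cumulative effect of these transient elevations on renal function". A similar reading of these rows would be weaker than it looks unless readers can see who was off drug and why.

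**Working it through.** The documents give no expected laboratory event rate and no formal sample-size basis (Protocol 11.1), so there is no figure of the plan's own to reproduce. The size is an illustration.

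**From the documents:** 8 post-baseline visits (Protocol 14.1.7); about 200 patients (Protocol 5.1).

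**Assumed:** at scheduled visit k, a share h_k of patients on drug has a new Table 2 value; the drug is then stopped; values are normal while off drug; a share q of stopped patients is still off drug, but attending, at each next visit.

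**Formulas.** With f_k the share off drug at visit k and f_1 = 0:
- f_(k+1) = q × [f_k + (1 − f_k) × h_k]
- all-values row = h_k × (1 − f_k); on-drug row = h_k
- relative understatement = f_k
- ever abnormal by visit k = 1 − product of (1 − h_j) for j = 1 to k

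**Worked case:** h = 2%, q = 1, Week 96 (k = 8). f_8 = 1 − 0.98^7 = 13.2%. All-values row = 2% × 0.98^7 = 1.74%, against 2.00% on drug. Ever abnormal = 1 − 0.98^8 = 14.9%, about 30 of 200.

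| h per visit | All-values row, Week 12 to 96, q = 1 | On-drug row, Week 96 | Understatement, Week 96: q = 0.5 / q = 1 | Understatement, Week 48, q = 1 | Ever abnormal by Week 96 |
|---|---|---|---|---|---|
| 1% | 1.00% to 0.93% | 1.00% | 1% / 7% | 3% | 7.7% |
| 2% | 2.00% to 1.74% | 2.00% | 2% / 13% | 6% | 14.9% |
| 5% | 5.00% to 3.49% | 5.00% | 5% / 30% | 14% | 33.7% |
| rising 0.5% to 4% | 0.50% to 3.47% | 4.00% | 3% / 13% | 3% | 16.7% |
| rising 1% to 8% | 1.00% to 6.00% | 8.00% | 6% / 25% | 6% | 31.0% |

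If every stopped patient has restarted by the next visit (q = 0), there is no understatement.

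**What this shows.**
1. Off-drug values lower the later rows, modestly unless almost everyone stays off.
2. With a rising risk, the all-values row still rises.
3. With a constant risk, the on-drug row is flat as well. Restricting to on-drug samples does not reveal accumulation; the ever-abnormal column does.

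**Limits.**
- Trigger values found at unscheduled tests miss the scheduled-visit rows altogether, so masking could be larger. Whether the worst-grade table takes them depends on a period of interest that the SAP does not define.
- Samples taken while off ataluren for nephrotoxic IV antibiotics may themselves be raised, which would push a row up.
- Relocated early-termination values are not modelled.
- Week 96 may lie out of reach. The first Study 021 patient started on 15 August 2014 (Protocol 1), and 48 weeks later is 17 July 2015. From there to 2 March 2017 (SAP 2.1) is 594 days, or 84.9 weeks. If discontinuation took effect on that date and the extension followed without a gap, no one reached Week 96, and the smaller Week 48 figures matter more.

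**The case against.** A reader might go further and infer that the tables turn cumulative toxicity into a low, flat rate. At h = 2%, q = 1 and Week 72, 1 − 0.98^6 = 11.4% have ever been affected, while the row shows 2% × 0.98^5 = 1.8%, about a six-fold gap. The documents do not support that inference, for four reasons.

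- The two figures measure different things: cumulative incidence and prevalence at one visit. Removing off-drug samples moves 1.8% only to 2.0%, which is 0.2 of the 9.6 points between them.
- A trigger value found at a scheduled visit stays in that visit's row. Where stopping awaits confirmation, the Table 2 footnote can place a second abnormal on-drug value in the next row.
- Staying off drug while attending is not the usual path. Protocol 6.3.3 directs patients with probably related hepatic or renal events to discontinuation and recommends restarting after unrelated ones; only possibly related events are left to judgment. IV-antibiotic interruptions last for the course plus at least 2 days (Protocol 7.1.2), and 5 of the 7 Study 009 patients with renal serious events restarted (Protocol 14.2.4).
- Injury that does not recover after stopping stays visible in all-values tables. An on-drug table alone would drop those patients.

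It can also be said that all-data analysis is declared, that the SAP never labels these rows as on-treatment, and that abnormalities needing work-up become adverse events with onset dates (Protocol 9.1.1 and 9.3) and so enter the adverse-event rates. All of that stands. It limits the point to seven parameters and to the time course. It does not supply a planned table of when laboratory abnormality first occurs on drug, and the worst-grade and maximal-change tables have no time axis.

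**Conclusion.** The point holds in a limited form. For the Table 2 parameters, the by-visit rows combine samples taken on drug, during interruption and possibly after the last dose, and interruption depends in part on the tabulated values. The rows describe prevalence under a stop-and-recover policy. Under the assumed rates, the Week 96 understatement runs from none (all restart) through 1% to 6% of the row (half still off) to 7% to 30% (all stay off and attend). At Week 48 the worst case is 3% to 14%. Whether an abnormality ever occurred is not hidden. What is missing as a commitment is the time course of first abnormality by time on drug, for an endpoint that names timing. This is an inexpensive improvement to a descriptive safety analysis; it does not invalidate the planned tables.

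**What to change.** 1. Flag each laboratory value as on drug, interrupted, or after last dose, using the dosing and interruption records behind SAP 4.9. Their dates are not stated to be available; that is an inference from the planned interruption summaries. Take the flag from those records and not from the values, because the stopping recommendations are to be applied flexibly. Apply it also to early-termination values moved under SAP 5.2.
2. For the seven Table 2 parameters, keep the all-values by-visit summaries and shift tables. Beside them give an on-drug version, with counts at each visit of patients off ataluren or discontinued, by reason: Table 2 value, IV antibiotics, other.
3. Replace the as-necessary description by exposure with a firm table of cumulative incidence of first Table 2 threshold value by time on drug. Include unscheduled samples, give on-drug person-time, and define the period of interest.

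**Cost:** SAP wording and programming, with no new data collection if the dates are held and no change to clinical management. The on-drug version has a slightly smaller n and drops patients who stopped, so it must be read beside the all-values table.
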